8.2 Duration, On-study Event calculations

The duration between two dates will be calculated as [later date] – [earlier date] + 1 day. Study Day 1 or first dose date is the date of first study medication. Study day associated with an assessment will be calculated as [assessment date] – [first dose date (or enrollment date for non-treated subjects)], if the assessment is before first dose/enrollment; [assessment date] – [first dose date (enrollment for non-treated subjects)] + 1, if the assessment is on or after first dose/enrollment.

Events will be considered as occurring within X days (e.g., deaths within 30 days, deaths and AEs within 90 days) of last dose of study medication if [event date] – [last dosing date] ≤ X.

The following factors will convert days to months or years: 1 month = 30.4375 days, 1 year = 365.25 days.

8.3 Conventions for Partial/Missing Dates

Unless specified otherwise the following conventions will be used for imputing partial dates:

- If only the day of the month is missing, the 15th of the month will be used to replace the missing day.
- If both the day and the month are missing, “July 1” will be used to replace the missing information.
- If a date is completely missing, it will be considered as missing.

For date of death:

- If only the day of the month is missing, the 1st of the month will be used to replace the missing day*.
- If both the day and the month are missing, “Jan 1” will be used to replace the missing information*.
- If date is missing, death date will be imputed as the last known alive date.
 - * The imputed death date will be compared with the last known alive date (date of censoring for survival). If the death date is not equal to the date of censoring for survival then the maximum of the (imputed death date, date of censoring for survival) will be considered as the date of death.

For date of progression:

- If only the day of the month is missing, the 1st of the month will be used to replace the missing day*.
- If the day and month are missing or a date is completely missing, it will be considered as missing.
 - * In case, the date of death is present (complete date), the imputed progression date will be compared with the date of death. The minimum of the (imputed progression date, date of death) will be considered as the date of progression.

For date of last tumor assessment:

- If only the day of the month is missing, the 1st of the month will be used to replace the missing day*.
- If the day and month are missing or a date is completely missing, it will be considered as missing.
 - * In case, the date of death is present (complete date), the imputed date will be compared with the date of death. The minimum of the (imputed date, date of death) will be considered as the date of last tumor assessment.

For adverse events of special interest onset date:

- If only the day of the month is missing, the first of the month will be used to replace the missing day.
- If the day and month are missing or a date is completely missing, it will be considered as missing.

For adverse events of special interest resolution date:

- If only the day of the month is missing, the last of the month will be used to replace the missing day.
- If the day and month are missing or a date is completely missing, it will be considered as missing.

Otherwise, missing values will not in general be imputed.

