1.4.2 Adverse Effects with Nivolumab Therapy

Two studies have contributed to most of the monotherapy clinical experience with nivolumab in subjects with melanoma and other solid malignancies. CA209001 was a Phase 1 single-dose dose escalation study in 39 subjects with previously treated advanced or metastatic cancer. Subjects received a single dose of nivolumab at 0.3, 1, 3, or 10 mg/kg with an option for retreatment at 3 months. CA209003 is an ongoing Phase 1 open-label, multiple dose escalation study in 304 subjects with select previously treated advanced solid tumors, including melanoma, RCC, NSCLC, colorectal cancer, and hormone-refractory prostate cancer. Subjects received nivolumab at doses of 0.1, 0.3, 1, 3 or 10 mg/kg intravenously every 2 weeks, up to a maximum of 2 years of total therapy. As of 03-Jul-2012, a total of 107 melanoma subjects were treated with nivolumab in the dose range of 0.1-10 mg/kg.

Adverse Events

Treatment-related AEs were reported in 230 (75.2%) of the 306 patients in the CA209003 study. The most frequently reported treatment-related AEs were fatigue (28.1%), rash (14.7%), diarrhea (13.4%), and pruritus (10.5%) (Table 1.4.2-1). Of the AEs, most were low-grade (Grade 1 to Grade 2) with relatively few related high-grade (Grade 3 to Grade 4) AEs reported in 52 (17.0%) patients. The most frequently reported treatment-related, high-grade AE was fatigue (6.5%). Most high-grade events were manageable with the use of corticosteroids or hormone replacement therapy (endocrinopathies).

The one exception is pulmonary inflammation AEs, which may be numerically greater in patients with NSCLC because, in some cases, it can be difficult to distinguish between nivolumab-related and unrelated causes of pulmonary symptoms and radiographic changes.

Due to the immune mechanism of action of nivolumab, there are select AEs that require more frequent monitoring and/or unique intervention, such as immunosuppression. These adverse events of special interest (AEOSIs) include GI AEs, pulmonary AEs, renal AEs, hepatic AEs, skin AEs, endocrinopathies, and infusion reactions. Each category is composed of a discrete set of preferred terms, and AE management algorithms have been developed for suspected pulmonary toxicity, diarrhea or suspected colitis, hepatotoxicity, endocrinopathy, and nephrotoxicity. These may be found in the investigators brochure for nivolumab.

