6 STUDY PERIODS, TREATMENT REGIMENS AND POPULATIONS FOR ANALYSES

6.1 Study Period

See Section 6.1 of the Core Safety SAP.

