APPENDIX 1 SELECT ADVERSE EVENTS DEFINITION AND CONVENTIONS

The select Adverse Events (select AEs) consist of a list of preferred terms grouped by specific category (e.g. pulmonary events, gastrointestinal events categories) and by subcategory (e.g. pituitary disorders, diabetes, thyroid disorders, adrenal disorders subcategories). These categories and subcategories are defined by the Sponsor and the list that is most current at the time of analysis will be used. Also, changes may be made to this list with each new version of MedDRA.

For information, the select adverse events defined at the time of finalization of the first version of the document are listed in [Table 5](#) using MedDRA version 18.1. The final list used for the clinical study report will be included in an Appendix of the CSR.

Time-to onset definition

Time-to onset of select AE (any grade) for a specific category (i.e. pulmonary events, gastrointestinal events, endocrine adverse event, hepatic adverse event, hypersensitivity/infusion reaction, renal adverse event, skin adverse event) is defined as the time between the day of the first dose of study treatment and the onset date of the earliest select AE (of any grade) in this category.

If the subject did not experience a select AE (of any grade) in the category, time-to onset will be censored at the maximum follow-up time of all subjects in their respective treatment group (i.e. for subjects without an event, follow-up time is defined from first dosing date up to last dosing date +30 days (or 100 days depending on the analysis) if subjects are off treatment and followed for at least 30 days (or 100 days depending on the analysis) , otherwise it is defined up to the last known alive date). The resulting Kaplan-Meier plot will represent the cumulative rate of the select AE (any grade) in the category over time.

Time-to onset of select AE (grade 3-5) for a specific category is defined similarly but restricted to grade 3-5 select AEs.

Time-to onset of drug-related (grade 3-5 or any grade) select AE for a specific category is defined similarly but restricted to drug-related select AEs.

Time-to onset for a specific subcategory is defined similarly but restricted to event of this subcategory.

Time-to resolution definition

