In order to derive the time-to resolution, overlapping or contiguous select AEs within a specific category (defined in [Table 5](#)) will be collapsed into what will be termed “clustered” select AEs. For example, if a subject (without pre-treatment AE) experienced an AE from 1st to 5th January, another AE (with different PT but within same category) from 6th to 11th January and same AE from 10th to 12th January, these will be collapsed into one clustered select AE from 1st to 12th January. [Table 4](#) is summarizing key derivation steps for each type of clustered select AEs.

Time-to resolution of select AE (any grade) for a specific category is defined as the longest time from onset to complete resolution or improvement to the grade at baseline among all clustered select AEs in this category experienced by the subject. Events which worsened into grade 5 events (death) or have a resolution date equal to the date of death are considered unresolved. If a clustered select AE is considered as unresolved, the resolution date will be censored to the last known date alive. Improvement to the grade at baseline implies that all different AE events in the clustered

select adverse event should at least have improved to the corresponding (i.e with same preferred term) baseline grade. This measure is defined only for subjects who experienced at least one select AE in the specific category.

The time-to resolution of select AE (grade 3-5) for a specific category is defined similarly with an onset date corresponding to a grade 3-5 select AE.

Time-to resolution of drug-related select AE (any grade or grade 3-5) is defined similarly but restricted to drug-related select AE.

The time-to resolution of select AE (any grade or grade 3-5, drug-related or all) where immune modulating medication was initiated is defined similarly with the additional condition that the subject started an immune modulating medication during the longest select AE resolution period.

Time-to resolution for a specific subcategory is defined similarly but restricted to event of this subcategory.

Table 4: Derivation of Clustered Select AE

Type of clustered select AE	Derivation
Any grade	
 • Collapse any on-treatment select AE from the same category
Drug-related of any grade	
 • Collapse any on-treatment drug-related select AE from the same category

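### SAP 8.3 dates a select AE with a missing onset day to the first of the month without a floor at first dose, so an event in the month of first dose can be dated before treatment

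*SAP*

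**What the plan says.** SAP 8.3 has a specific rule for the onset of adverse events of special interest: "If only the day of the month is missing, the first of the month will be used to replace the missing day". If the month is missing too, the onset is left missing. The rule stops there.

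The same section checks other imputed dates against a known date. For death, "the maximum of the (imputed death date, date of censoring for survival) will be considered as the date of death". For progression, "The minimum of the (imputed progression date, date of death) will be considered as the date of progression". The date of last tumor assessment is also capped at the date of death.

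The protocol uses the term for the select AEs. Section 1.4.2 introduces the select AEs and continues: "These adverse events of special interest (AEOSIs) include GI AEs, pulmonary AEs, renal AEs". Its full list has the same seven categories as SAP 4.1.

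Three other parts of the SAP use the imputed onset:
- SAP 8.2 sets the origin: "Study Day 1 or first dose date is the date of first study medication". An earlier date gets a negative study day.
- SAP Appendix 1 says that time to onset "is defined as the time between the day of the first dose of study treatment and the onset date of the earliest select AE".
- SAP Appendix 1, Table 4, builds the clusters for time to resolution by the instruction "Collapse any on-treatment select AE from the same category".

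SAP 6.1 does not define the study periods itself. It says only "See Section 6.1 of the Core Safety SAP".

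**The concern.** A patient first dosed late in a month who has a select AE a few days later, recorded with month and year only, is given an onset before the first infusion. For most such records this is an artefact. Protocol 6.2.1 starts collection of nonserious AEs at the first dose, and a treatment-related event cannot precede treatment. Only SAEs are collected from consent (Protocol 6.1.1), so a true pre-dose onset is possible for those.

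The part at stake for certain is time to onset, a secondary endpoint in Protocol 8.3.2 and SAP 4.2. It is measured from first dose and has no meaning for an onset before it. Time to resolution, also secondary, is affected in one of two ways. If the on-treatment window opens at first dose, the event is left out of the cluster. If it does not, the duration includes days before treatment.

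**Working it through.** **The plan's own figure, for scale only.** The point rests on no stated figure. SAP 5 gives, for about 3 events in 640, a 95% CI of 0.1% to 1.4%, and for about 2 events 0% to 1.1%. Exact (Clopper-Pearson) limits reproduce both: 3/640 = 0.47% (0.10% to 1.36%) and 2/640 = 0.31% (0.04% to 1.12%).

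**One record (dates assumed).** First dose 20 September, true onset 27 September, resolved 30 September, onset day missing.

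| | Onset used | Study day of onset | Onset to resolution, counted as in SAP 8.2 |
|---|---|---|---|
| Truth | 27 Sep | 27 − 20 + 1 = 8 | 30 − 27 + 1 = 4 days |
| SAP 8.3 as written | 1 Sep | 1 − 20 = −19 | 30 − 1 + 1 = 30 days |
| With a floor | 20 Sep | 20 − 20 + 1 = 1 | 30 − 20 + 1 = 11 days |

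If the SAP 8.2 duration formula (later minus earlier plus 1) is applied mechanically to the row as written, time to onset becomes 20 − 1 + 1 = 20 days. That is positive and plausible, and wrong.

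**Share of same-month records affected.** Assume every first-dose date in a 365-day year is equally likely, and onset is 0 to 30 days later in the same calendar month.
- A month of L days has L(L + 1)/2 such pairs. Over the year: 7 × 496 + 4 × 465 + 406 = 5,738.
- The imputed date is not before first dose only when the first dose is on the 1st. Those pairs number L per month, 365 in all.
- Share dated before first dose: 1 − 365/5,738 = 93.6%, about 94%.
- These imputed onsets precede first dose by 10.5 days on average and by 30 at most.

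By true lag from first dose, without conditioning on the same month, the chance of a pre-dose imputed date is 97% at day 0, 74% at day 7, 51% at day 14, 28% at day 21 and 5% at day 28. It averages 47% over days 0 to 30.

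If the general mid-month rule of SAP 8.3 applied instead, pairs with first dose after the 15th would be misdated: (7 × 136 + 4 × 120 + 91)/5,738 = 1,523/5,738 = 27%. That rule has no floor either.

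**How many events.** The documents give no rate of missing onset days, so this is a range on assumptions. Take 40 Grade 3-4 select AEs as an upper figure: under 5% in the earlier Phase 3 study (Protocol 1.4.3), times about 800 treated (Protocol 8). With exponential onset of mean m months and a uniform dosing day, the share in the first-dose calendar month is q = 1 − m(1 − e^(−1/m)). This gives 0.368, 0.150 and 0.079 for m = 1, 3 and 6. Affected events = 40 × (share with day missing) × q, counting every same-month event as affected:

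| Day missing (assumed) | m = 1 | m = 3 | m = 6 |
|---|---|---|---|
| 1% | 0.15 | 0.06 | 0.03 |
| 5% | 0.74 | 0.30 | 0.16 |
| 10% | 1.47 | 0.60 | 0.32 |

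Appendix 1 also defines time to onset for select AEs of any grade. Those are more numerous, so the counts there would be higher.

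**The case against.** The strongest reply is that a rule absent from SAP 8.3 may stand elsewhere. The opening of SAP 8 allows further conventions in the Data Presentation Plan. SAP 7.1 and 7.6.2.2 send general AE methods, and the incidence, onset and resolution of select AEs, to the Core Safety SAP. That is fair, and neither document can be checked here. But SAP 8.3 states its own rule for these events and points to no other, so a programmer who follows it gets the wrong date.

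Missing days should also be rare for early severe events. AEs are assessed every two-week cycle, SAEs are reported within 24 hours, and blank CRF fields are restricted. A median is also robust to an early onset moved still earlier. Both points stand, and they limit the size.

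A reader might go further and infer that affected events drop out of the primary incidence and bias it downwards. The documents do not support this:
- SAP 7.6.1.1 counts treated subjects with the event and states no time window. Protocol 8.4.2.1 reports the primary endpoint both during and off treatment.
- The explicit on-treatment filter, in Table 4, serves time to resolution only.
- The within-X-days test in SAP 8.2 has an upper limit only, so a pre-dose date passes it.
- The rule does not err in one direction only. With a last dose on 10 June and a true onset on 25 July (45 days later), a missing day gives 1 July (21 days later). This brings a late event inside a 30-day window.

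The fall from 0.47% to 0.31% when one of three events is lost is likewise not an expected effect. It assumes that a whole event is lost from one rare AE.

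**Conclusion.** The gap is real and minor. Taken literally, SAP 8.2, SAP 8.3 and Appendix 1 together give an onset before Study Day 1 for about 94% of select AEs that occur in the calendar month of first dose with the day missing. That share assumes uniform dates. Time to onset is then invalid whatever the Core Safety SAP says about study periods, unless that document or the Data Presentation Plan overrides the date rule.

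Loss from the time-to-resolution clusters follows only if the on-treatment window opens at first dose. An effect on the primary incidence is not shown, because it depends on a window in a document not supplied. The number of affected events cannot be computed. On the assumed ranges above it runs from well under one to about 1.5 of at most 40 Grade 3-4 events.

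**What to change.** Add one sentence to SAP 8.3, under the onset rule for adverse events of special interest:

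> If only the day is missing, the month and year of onset equal those of first dose, and the imputed date precedes first dose, onset is set to the first dose date, unless the record (for example, a resolution date before first dose) shows that the event began before treatment.

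The exception protects true pre-dose SAEs. With the floor, the share of same-month records misdated before first dose falls from about 94% to 0%, apart from those shown to be pre-treatment. The affected events take Study Day 1, which can still be earlier than the true day.

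Do not extend the floor to onsets with day and month both missing. SAP 8.3 leaves those missing, and a Day 1 onset could be months too early.

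If the Core Safety SAP or the Data Presentation Plan already has this rule, cite it in SAP 8.3 instead. The cost is one sentence and one line of derivation code, with no change to data collection or sample size.

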Grade 3-5	
 • Collapse any on-treatment select AE from the same category. • Resolution will be based on the onset date of the earliest grade 3-5 records (if no grade 3-5 record, clustered select AE is excluded)
Drug-related of Grade 3-5	
 • Collapse any on-treatment drug-related select AE from the same category • Resolution will be based on the onset date of the earliest grade 3-5 record (if no Grade 3-5 record, clustered select AE is excluded)

The algorithm for collapsing select adverse event records is using the following conventions:

For each subject and specified category, the corresponding adverse event records will be collapsed when:

- 1) Multiple adverse event records have the same onset date.
- 2) The onset date of an event record is either the same day or 1 day later than the resolution date of a preceding event record (contiguous events).
- 3) The onset date of an event record is after the onset date and prior to or on the resolution date of a preceding event record (overlapping events).

Table 5: Select Adverse Events

Category	Subcategory	Preferred Term
ENDOCRINE ADVERSE EVENT	ADRENAL DISORDER	ADRENAL INSUFFICIENCY
		ADRENAL SUPPRESSION
		ADRENOCORTICAL INSUFFICIENCY ACUTE
		BLOOD CORTICOTROPHIN DECREASED
		BLOOD CORTICOTROPHIN INCREASED
		HYPOTHALAMIC PITUITARY ADRENAL AXIS SUPPRESSION
		SECONDARY ADRENOCORTICAL INSUFFICIENCY
	DIABETES	DIABETES MELLITUS
		DIABETIC KETOACIDOSIS
		FULMINANT TYPE 1 DIABETES MELLITUS
		LATENT AUTOIMMUNE DIABETES IN ADULTS
		TYPE 1 DIABETES MELLITUS
	PITUITARY DISORDER	HYPOPHYSITIS
		HYPOPITUITARISM
		LYMPHOCYTIC HYPOPHYSITIS
	THYROID DISORDER	ATROPHIC THYROIDITIS
		AUTOIMMUNE HYPOTHYROIDISM
		AUTOIMMUNE THYROIDITIS
		BASEDOW'S DISEASE
		BLOOD THYROID STIMULATING HORMONE DECREASED
		BLOOD THYROID STIMULATING HORMONE INCREASED
		HYPERTHYROIDISM
		HYPOTHYROIDISM

Table 5: Select Adverse Events

Category	Subcategory	Preferred Term
		PRIMARY HYPERTHYROIDISM
		PRIMARY HYPOTHYROIDISM
		THYROID FUNCTION TEST ABNORMAL
		THYROID HORMONES DECREASED
		THYROID HORMONES INCREASED
		THYROIDITIS
		THYROIDITIS ACUTE
		THYROXINE DECREASED
		THYROXINE FREE DECREASED
		THYROXINE FREE INCREASED
		THYROXINE INCREASED
		TRI-IODOTHYRONINE UPTAKE INCREASED
GASTROINTESTINAL ADVERSE EVENT		AUTOIMMUNE COLITIS
		COLITIS
		COLITIS ULCERATIVE
		DIARRHOEA
		ENTERITIS
		ENTEROCOLITIS
		FREQUENT BOWEL MOVEMENTS
		GASTROINTESTINAL PERFORATION

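### A select AE resolution date with a missing day is set to month end with no upper bound, so it can fall after death without being caught by the Appendix 1 test for unresolved events

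*SAP*

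**What the plan says.** Under the entry "For adverse events of special interest resolution date", SAP 8.3 gives this rule: "If only the day of the month is missing, the last of the month will be used to replace the missing day". If the month is missing too, or the whole date, the date stays missing. The entry does not compare the imputed date with death, last known alive date or data cut-off.

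Other entries in the section do make such a comparison. For progression: "The minimum of the (imputed progression date, date of death) will be considered as the date of progression". For the last scan: "The minimum of the (imputed date, date of death) will be considered as the date of last tumor assessment". Both apply when the date of death is complete. An imputed death date is in turn not allowed to fall before the last known alive date.

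SAP Appendix 1 has its own rule for events running up to death: "Events which worsened into grade 5 events (death) or have a resolution date equal to the date of death are considered unresolved". An unresolved event is censored at the last known date alive.

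SAP 8.3 speaks of events of special interest and Appendix 1 of select AEs. Protocol 1.4.2 supplies the link: "These adverse events of special interest (AEOSIs) include GI AEs, pulmonary AEs, renal AEs, hepatic AEs, skin AEs, endocrinopathies, and infusion reactions". Those seven groups match the seven categories in SAP Table 5. Median time to resolution of select AEs is a secondary endpoint (Protocol 8.3.2, SAP 4.2).

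**The concern.** Progression and last-scan dates are imputed to the 1st of the month, which seldom overshoots death, and yet they are capped. The resolution date is imputed to month end, the choice most likely to overshoot, and it is not capped. The one safeguard, in Appendix 1, tests for equality with the date of death and says nothing about a later date.

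Such a record would contribute a resolution on a day when the patient was already dead. Appendix 1 also takes each patient's longest cluster in a category, so an inflated duration is more likely to be the one analyzed. At stake is the description of how select AEs resolve in patients who die soon after one.

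**Working it through.** **1. The rules side by side (SAP 8.3).**

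| Date with missing day | Imputed to | Bound |
|---|---|---|
| Progression | 1st of month | not after a complete date of death |
| Last tumor assessment | 1st of month | not after a complete date of death |
| Death | 1st of month | not before last known alive date |
| Select AE resolution | last of month | none stated |

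**2. When the imputed date passes death.** Take a partial resolution date in the month of death. Overshoot = last day of the month − day of death. It is zero only if death fell on the last day. Over 2015–2018 there are 4 × 12 = 48 month-end days among 1,461 calendar days:

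- equal to death: 48/1,461 = 3.3%
- after death: 1,413/1,461 = 96.7%
- largest overshoot: 31 − 1 = 30 days
- mean overshoot: 14.7 days over all days, 15.2 days when it is above zero

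This treats every calendar day as equally likely for death. It is conditional on a partial date in the month of death and is not a frequency of affected patients.

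**3. The Appendix 1 test applied.** Assumed dates: onset 20 Feb 2016, death 12 Mar 2016, resolution reported as March 2016, not Grade 5. Duration = later − earlier + 1 (SAP 8.2).

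- As written: imputed 31 Mar, which differs from 12 Mar, so the event is resolved at 40 + 1 = 41 days, 31 − 12 = 19 days after death.
- Capped at death, event recorded as resolved: duration 21 + 1 = 22 days, an upper bound.
- Capped at death, event recorded as open: unresolved and censored at 22 days, if last known alive on the day of death.

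**4. Day of death also missing.** Death moves to the 1st (or to the last known alive date if later) and resolution to month end, so the gap can again reach 30 days. A cap at the date of death alone would then rest on another imputed date.

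**5. How many records.** The documents give no count. An illustration: Protocol 1.4.3 reports fewer than 5% of nivolumab patients with Grade 3–4 select AEs in the earlier Phase 3 trial after ipilimumab, and Protocol 8 plans about 800 treated patients.

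- 5% × 800 = at most about 40 patients
- assume 1–5% have a partial resolution date: 0.4 to 2 patients
- assume 10% of those fall in the month of death: 0.04 to 0.2 patients across all categories

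The 1–5% and 10% are assumptions. Any-grade summaries would start from more events.

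**The case against.** The strongest reply is that an event still open at death will normally have no resolution date, which stays missing, or will be closed on the date of death, which Appendix 1 catches. A month and year without a day more naturally mean that the event did resolve that month. Resolved is then the right status, and the only error is a duration up to 30 days too long. This stands, and it is why the point is minor. It does not remove the impossible duration.

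A reader might infer three stronger things that the documents do not support:

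- **That the rule systematically turns events open at death into resolved ones.** That needs a site to record a resolution month for an event that had not resolved. The text allows it, but nothing shows it to be the usual case.
- **That 96.7% measures how often this happens, or that a category median will move.** The percentage only says that most days are not month ends. One or two affected patients in a single category would be needed, and the illustration above expects fewer than one in all.
- **That a cap cures false merging of events.** Appendix 1 joins records when "The onset date of an event record is either the same day or 1 day later than the resolution date" of the preceding record, so a month-end date can absorb a separate later event in any living patient. A patient alive past month end keeps the same imputed date with or without the cap.

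SAP 7.6.2.2 also sends time to resolution to Section 7.6.6 of the Core Safety SAP, and SAP 8 says that further conventions may be in the Data Presentation Plan. Neither was available. Either could hold a cap, though the SAP 8.3 entry points to none.

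**Conclusion.** The gap is real on the text supplied, and it is minor. A partial resolution date in the month of death is placed after death, by up to 30 days, unless death fell on the last day of the month, and the equality test in Appendix 1 misses it. The duration is then impossible. The status is also wrong if the event was in fact open at death. For patients alive at last contact or cut-off, a reported resolution remains a resolution and only the duration can be too long.

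The effect is confined to time to resolution, a secondary endpoint. The primary incidence of high-grade, treatment-related select AEs does not use this date. The conclusion rests on reading special-interest events as select AEs (Protocol 1.4.2) and on the Core Safety SAP and Data Presentation Plan holding no cap. The number of records is unknown and probably very small.

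**What to change.** - **SAP 8.3:** set the imputed resolution date to the earliest of month end, the date of death (if complete), the last known alive date and the data cut-off. Apply this before clustering. If the bound lies before the reported month, the record contradicts itself and should be queried.
- **Appendix 1:** for reported resolution dates, widen the test from equality with the date of death to any date on or after it.
- **Capped partial dates:** take resolved or unresolved status from the recorded AE outcome, not from the date. Otherwise the cap followed by the date test would censor events that truly resolved earlier in the month of death. This assumes that the AE form records outcome; the documents do not show the form.
- **First check** whether Core Safety SAP 7.6.6 already holds such a bound. If it does, a cross-reference in SAP 8.3 may be enough.

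The cost is a few SAP sentences and a few lines of derivation code. One small downside remains: resolved events capped in this way keep an upper-bound duration.
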